APPENDIX 10. CAIRO-BISHOP CRITERIA FOR DIAGNOSIS OF TUMOR LYSIS SYNDROME

For a diagnosis of laboratory tumor lysis syndrome (TLS), 2 or more of the metabolic abnormalities shown in Table 25 must be present during the same 24-hour period within 3 days before the start of therapy, or up to 7 days after. Clinical TLS requires the presence of laboratory TLS plus an increased creatinine, seizures, cardiac dysrhythmia, or death.

Table 25: Definitions of Laboratory and Clinical Tumor Lysis Syndrome

Metabolic Abnormality	Criteria for Classification of Laboratory TLS	Criteria for Classification of Clinical TLS
Hyperuricemia	Uric acid >8.0 mg/dL (475.8 µmol/L) in adults or above the ULN for age in children	
Hyperphosphatemia	Adults: phosphorus >4.5 mg/dL (1.5 µmol/L) Children: phosphorus >6.5 mg/dL (2.1 µmol/L)	
Hyperkalemia	Potassium >6.0 mmol/L	Cardiac dysrhythmia or sudden death probably or definitely caused by hyperkalemia
Hypocalcemia	Corrected calcium <7.0 mg/dL (1.75 mmol/L) or ionized calcium <1.12 (0.3 mmol/L) ^a	Cardiac dysrhythmia, sudden death, seizure, neuromuscular irritability (tetany, paresthesias, muscle twitching, carpopedal spasm, Trousseau's sign, Chvostek's sign, laryngospasm, or bronchospasm), hypotension, or heart failure probably or definitely caused by hypocalcemia
Acute kidney injury ^b	Not applicable	Increase in serum creatinine level of 0.3 mg/dL (26.5 µmol/L) (or single value >1.5 times the ULN of the age-appropriate range if no baseline creatinine measure is available) or the presence of oliguria, defined as an average urine output of <0.5 ml/kg/hr for 6 hr

Abbreviations: hr = hour; TLS = tumor lysis syndrome; ULN = upper limit of normal.

^a The corrected calcium level in mg/dL = measured calcium level in mg/dL + 0.8 × (4 – albumin g/dL).

^b Acute kidney injury is defined as an increase in the creatinine level of at least 0.3 mg/dL (26.5 µmol/L) or a period of oliguria lasting 6 hr or more. By definition, if acute kidney injury is present, the patient has clinical TLS. See Levin et al for data about acute kidney injury.

Reference: [Howard 2011](#).

Signature Page for VV-CLIN-000078 v14.0

Approval	[name] Medical 30-Jan-2024 22:35:50 GMT+0000
----------	--

Approval	[name] Regulatory 31-Jan-2024 04:13:21 GMT+0000
----------	--

Signature Page for VV-CLIN-000078 v14.0

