APPENDIX 3. SCHEDULE OF ASSESSMENTS - AML SUBJECTS ONLY – COMBINATION THERAPY (CONTINUED)

Abbreviations: AML = acute myeloid leukemia; ALP = alkaline phosphatase; ALT = alanine aminotransferase; ANC = absolute neutrophil count; aPTT = activated partial thromboplastin time; AST = aspartate aminotransferase; BP = blood pressure; BUN = blood urea nitrogen; CBC = complete blood count; CR = complete response; CT = computed tomography; ECG = electrocardiogram; ECOG = Eastern Cooperative Oncology Group; EOS = End of Study; Hct = hematocrit; HCV Ab = hepatitis C virus antibody; Hgb = hemoglobin; HIV = human immunodeficiency virus; HR = heart rate; ICF = informed consent form; INR = international normalized ratio; LDH = lactate dehydrogenase; MCH = mean corpuscular hemoglobin; PCR = polymerase chain reaction; PD = pharmacodynamic; PK = pharmacokinetic; PT = prothrombin time; RBC = red blood cell; RU = ramp-up; TLS = tumor lysis syndrome; WBC = white blood cell.

- a. **Study Assessment Day(s)** – C1D1 and visits when blood for pharmacodynamic/biomarker studies are collected should be conducted Monday through Wednesday if possible so that specimens can be shipped for receipt no later than a Friday. There is \pm 3-day window allowable for each clinic visit during Cycle 1. Following Cycle 1, the allowable window is up to 7 days prior and 2 days after the scheduled clinic visit and its associated assessments.
- b. **Screening** – Screening assessments are to be performed within 28 days before the first dose of venetoclax. Laboratory assessments need not be repeated on Day 1 if performed within the prior 72 hours. Physical examination need not be repeated on Day 1 if performed within the prior 7 days. Some tests performed prior to obtaining ICF (e.g., CT scan, bone marrow biopsy) may not need to be repeated for the study as long as they were performed within the allowed screening window.
- c. **Venetoclax Ramp-up** – applies to **combination Cohorts 12–19 and 21–25**. Venetoclax ramp-up dosing begins on Cycle 1 Day 1 at 100 mg and 200 mg on Day 2. Dosing continues at 200 mg on Days 3–21, then 400 mg on Days 22–28. Increasing venetoclax dose from 200 mg to 400 mg on Day 22 is not considered dose ramp-up.
- d. **Cycle 3 and subsequent cycles** – all cycles after Cycle 3 should follow the same schedule of activities as Cycle 3.

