### 8.7.2 Adverse Events (AE)

An AE is any untoward medical event that occurs to a subject following the start of study drug administration, whether or not the event is considered drug-related. Pre-existing conditions are not considered an AE unless the condition worsens by at least one grade following the start of study drug administration. Adverse events will be captured from the first dose of study drug and continue until 30 days after the last dose, or until a subsequent anti-cancer therapy is initiated if this occurs earlier than 30 days after the last study drug dose.

Treatment-emergent adverse events (TEAEs) are defined identically as AEs in this study.

An SAE is an AE that results in any of the following outcomes:

- Death
- A life-threatening condition
- An inpatient hospitalization or prolongation of an existing hospitalization
- A persistent or significant disability/incapacity
- A congenital anomaly/birth defect
- Important medical events that may not be immediately life-threatening or result in death or hospitalization but may jeopardize the patient or may require intervention to prevent one of the other outcomes listed above

Elective hospitalizations not in response to an AE is not considered an SAE. Adverse events constituting an SAE will be reported beginning from the first dose of study drug.

All deaths within 30 days of the last dose of study drug that are an outcome of an AE should be reported. Deaths due to disease progression should be reported as such and not as SAEs..

An overview of AEs will be provided by dose cohort, disease group and in total, summarizing subject incidence of the following information:

- Any TEAEs
- Drug-related TEAEs
- CTCAE grade  $\geq 3$  TEAEs
- Drug-related CTCAE grade  $\geq 3$  TEAEs
- Deaths due to AEs
- Treatment-emergent SAEs
- Drug-related treatment-emergent SAEs

- Dose interruption due to TEAEs
- Dose interruption due to drug-related TEAEs
- Dose reduction due to TEAEs
- Dose reduction due to drug-related TEAEs
- Discontinuation of study drug due to TEAEs
- Discontinuation of study drug due to drug-related TEAEs

The number and percentage of subjects with TEAEs and Grade 3/4/5 TEAEs will be summarized for each dose cohort, tumor type, and in total by SOC and PT. For these summaries, subjects with multiple adverse events will be counted only once per SOC and PT.

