Additionally, the number and percentage of subjects with TEAEs will also be summarized by PT for each dose cohort, tumor type, and in total. Drug-related TEAEs, treatment-emergent SAEs, drug-related treatment-emergent SAEs, TEAEs leading to discontinuation of study drug, drug-related TEAEs leading to discontinuation of study drug, TEAEs leading to dose reduction/interruption of study drug, and drug-related TEAEs leading to dose reduction/interruption of study drug will be summarized in the same manner. For these summaries, subjects with multiple adverse events will be counted only once per PT.

Summaries will be provided by the worst CTCAE grade and PT for the number and percentage of subjects with TEAEs and drug-related TEAEs. Subjects with multiple adverse events will be counted only once by the highest CTCAE grade within a PT.

Furthermore, Tumor Lysis Syndrome (TLS) is considered AEs of special interest. The frequency and percentage of laboratory and clinical TLS (determined by Modified Cairo-Bishop criteria described in Appendix 10 of the protocol) will be tabulated by dose cohort, tumor type, and in total.

Listings will be provided for DLTs, SAEs, grade 3/4/5 AEs, AEs leading to dose reduction, AEs leading to dose interruption, AEs leading to discontinuation, and AEs leading to death. Additional listings may be provided for selected AEs of special interest. Moreover, a by-subject AE data listing including, but not limited to, verbatim, PT, SOC, CTCAE grade, action taken with voruciclib, and relationship to voruciclib will be provided.

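### SAP 8.7.2 counts TLS by a definition that opens 3 days before therapy, so its special-interest table can include TLS present before any study drug

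*Protocol*

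**What the plan says.** Protocol Appendix 10 diagnoses laboratory TLS when two or more of the abnormalities in its Table 25 "must be present during the same 24-hour period within 3 days before the start of therapy, or up to 7 days after". Table 25 uses fixed limits and does not compare the metabolic values with baseline. Clinical TLS is built on top of this: "Clinical TLS requires the presence of laboratory TLS plus an increased creatinine, seizures, cardiac dysrhythmia, or death".

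SAP section 8.7.2 states that "Tumor Lysis Syndrome (TLS) is considered AEs of special interest", and names no other event in that category. On how TLS is counted it says: "The frequency and percentage of laboratory and clinical TLS (determined by Modified Cairo-Bishop criteria described in Appendix 10 of the protocol) will be tabulated". The breakdown is per cohort, per tumor type and overall. The sentence sets no condition on onset after dosing or on worsening.

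Earlier in the same section the SAP gives its general rules: "An AE is any untoward medical event that occurs to a subject following the start of study drug administration", and "Pre-existing conditions are not considered an AE unless the condition worsens by at least one grade following the start of study drug administration". It defines treatment-emergent adverse events (TEAEs) as identical to AEs.

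**The concern.** The special-interest table is selected by one rule (Appendix 10), while the category it belongs to is defined by another (AE onset or worsening after the first dose). For the first three days of the Appendix 10 window the two rules cannot both be met. They can also differ after dosing, because a value that was already past its limit and has not changed still satisfies Appendix 10.

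Protocol section 4.9 describes TLS as a known risk with CDK9 inhibitors, and this is the one AE of special interest that the SAP names. The table is broken down by dose cohort, and the cohorts are small. A single case that reflects the subject's condition at entry would visibly change the TLS percentage at that dose.

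**Working it through.** Neither document states a TLS count or rate, so there is no figure to reproduce. The check sets the rules side by side and then does one division.

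**Inputs**

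- Window: 3 days before to 7 days after the start of therapy (Appendix 10).
- Limits for adults: uric acid above 8.0 mg/dL, phosphorus above 4.5 mg/dL, potassium above 6.0 mmol/L, or corrected calcium below 7.0 mg/dL, with an ionized-calcium alternative (Table 25).
- Pre-dose sampling: Protocol section 8.5 places Cycle 1 Day 1 tests before dosing. Appendix 3, footnote b adds: "Laboratory assessments need not be repeated on Day 1 if performed within the prior 72 hours". Since 72 h / 24 = 3 days, either panel falls in the pre-treatment part of the window. Footnote o shows that the panel contains all four analytes.
- Entry criteria: Protocol sections 3.1 and 3.2 set no limit on any of the four.
- Post-dose sampling in AML: 6 to 8 hours after each new venetoclax ramp-up dose, and 24 hours after the final one (Appendix 9).
- Cohort size: 3, possibly 4, extending to 6 (Protocol section 4.1). About 68 combination subjects are planned (Protocol section 10.1).

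**Step 1. Apply both rules to the same subject**

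| Pattern (two analytes, same 24 h) | Appendix 10 as written | AE rule in SAP 8.7.2 |
|---|---|---|
| Both past the limit before dosing, corrected afterwards | TLS | Not an AE |
| Both past the limit before dosing, unchanged after the first dose | TLS | Not an AE |
| One past the limit before dosing, the second only after | TLS | Can be an AE (syndrome begins after dosing) |
| Neither past the limit before dosing, both after | TLS | AE |

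The rules disagree on the first two rows.

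**Step 2. Does the general AE rule settle those rows?** The rule for pre-existing conditions needs a grade. Table 25 has limits but no grades, so one-grade worsening cannot be read from the composite. It has to be checked analyte by analyte, and the TLS sentence does not ask for that. SAP section 8.7.3 does: it defines treatment-emergent laboratory abnormalities as post-baseline and worse in CTCAE grade. The SAP therefore writes the condition out in one place and omits it in the other.

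**Step 3. Size.** One extra case in a group of n adds 100/n percentage points:

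- n = 3: 100/3 = 33.3 points
- n = 4: 100/4 = 25.0 points
- n = 6: 100/6 = 16.7 points
- n = 68: 100/68 = 1.5 points

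**Step 4. Which first dose?** Appendix 10 does not say which drug starts therapy. In combination cohorts venetoclax starts on Day 1 and voruciclib on Day 3. Using the SAP convention of no Study Day 0, the window is Day -3 to Day 8 on the first reading and Day -1 to Day 10 on the second. The second reading would place two days of venetoclax in the pre-treatment part. Protocol section 6.1 dates AEs in these cohorts from the first venetoclax dose.

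**The case against.** The strongest reply is that Appendix 10 says what TLS is, and SAP 8.7.2 says when an event is an AE. Read together, they already exclude pre-dose cases. Several passages support this. Protocol section 4.9 calls Appendix 10 diagnostic guidance. Protocol section 6.1 excludes disease-related laboratory values that have not changed since screening. Protocol section 9.5 defines a TEAE as starting or worsening after the first dose. The table shells are in a separate specification that may resolve the matter.

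This reply has force against a stronger reading that a reader might infer, namely that pre-treatment TLS will be reported as an effect of study drug. The documents do not support that reading. The general AE rules point the other way, the investigator judges relatedness separately for each AE (Protocol section 6.6), and drug-related TEAEs have their own summaries. Nor can pre-dose TLS enter dose escalation as a dose-limiting toxicity (DLT), because Protocol section 4.4 limits DLTs to TEAEs in Cycle 1.

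The reply does not remove the conflict. The SAP sentence tabulates TLS as determined by the criteria. It does not ask for reported TEAEs coded as TLS, so deriving the table from laboratory values with the full window is a fair reading.

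The likelihood of a pre-dose case is unknown. Appendix 9 requires prophylaxis for every subject and asks for existing abnormalities to be corrected before venetoclax. That makes a pre-dose case less likely, but also shows that the protocol expects some subjects to arrive with abnormal values.

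**Conclusion.** The concern holds as a conflict between two stated rules. A TLS table derived from Appendix 10 as written can include TLS that was present before any study drug, contrary to the AE and TEAE definition in the same SAP section. One such case would shift the TLS percentage by 33.3 points in a cohort of 3 and 16.7 points in a cohort of 6. Across the planned 68 combination subjects it would shift it by about 1.5 points.

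These sizes assume that a pre-dose case occurs and is counted. The documents give no pre-dose TLS rate, so no expected number of cases can be given. The effect is confined to the TLS tabulation: DLT determination and relatedness assessment are not touched. The SAP should be corrected because the ambiguity affects its one named AE of special interest and is cheap to remove.

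**What to change.** In SAP section 8.7.2, replace the bare reference to Appendix 10 with a counting rule:

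- **Laboratory TLS** is counted in the special-interest table only when (a) the qualifying 24-hour period falls after the first dose of study drug, taken as the first venetoclax dose in combination cohorts in line with Protocol section 6.1, and (b) at least one qualifying abnormality is new or at least one CTCAE grade worse than the last pre-dose value. New should mean not past its Table 25 limit at the SAP 7.2 baseline. Tying worse to one grade keeps the rule consistent with the SAP's own AE definition and stops trivial drift from counting.
- **Clinical TLS** is counted only when its clinical criterion begins after the first dose.
- **Subjects who met the criteria before dosing** appear in a separate baseline row.

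Under this rule the first two patterns in the table above go to the baseline row only, and the last two stay in the main count. If any of the four analytes cannot be graded from the collected data, the programming specification should say which comparison applies. SAP section 8.7.3 already has a fallback for tests without a grading scale.

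The cost is SAP wording and one extra baseline comparison in programming. No new data are needed, and the table specification is due to be finalized before database lock. The reported TLS count may become smaller, but the baseline row keeps the excluded cases visible.

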## LIST OF ABBREVIATIONS AND DEFINITIONS OF TERMS

| ABBREVIATION        | DEFINITION   |
|---------------------|--|
| AE                  | Adverse event  |
| AML                 | Acute myeloid leukemia   |
| ATC                 | Anatomical Therapeutic Classification                                      |
| CBC                 | Complete blood count   |
| CI                  | Confidence interval  |
| CDK9                | Cyclin-dependent kinase 9  |
| CLL                 | Chronic Lymphocytic Leukemia   |
| CR                  | Complete response  |
| CRF                 | Case report form   |
| CRi                 | Complete remission with incomplete marrow recovery                         |
| CTCAE               | Common Terminology Criteria for Adverse Events                             |
| DOR                 | Duration of response   |
| DOT                 | Duration of treatment  |
| DLBCL               | Diffuse Large B-cell Lymphoma  |
| DLT                 | Dose-limiting toxicity   |
| ECG                 | Electrocardiogram  |
| ECOG                | Eastern Cooperative Oncology Group   |
| ELN                 | European Leukemia Net  |
| EOS                 | End of Study   |
| FDG                 | Fluorodeoxyglucose   |
| FL                  | Follicular Lymphoma  |
| IgVH                | Immunoglobulin g heavy chain variable region                               |
| IP                  | Investigational product  |
| IS                  | Intermittent dosing schedule   |
| IS 1w,3w | Intermittent dosing schedule of 1 week on therapy and 3 weeks off therapy  |
| IS 2w,2w | Intermittent dosing schedule of 2 weeks on therapy and 2 weeks off therapy |
| IWCLL               | International workshop on CLL  |
| mBED                | Minimum biologically effective dose  |
| MCL                 | Mantle Cell Lymphoma   |
| MedDRA              | Medical Dictionary for Regulatory Activities                               |
| MTD                 | Maximum tolerated dose   |
| MZL                 | Marginal Zone Lymphoma   |
| NCI                 | National cancer institute  |
| ORR                 | Overall response rate  |
| PD                  | Progressive disease  |
| PFS                 | Progression-free survival  |

| ABBREVIATION | DEFINITION  |
|--------------|---|
| PR           | Partial response                                  |
| PT           | Preferred term                                    |
| QTcF         | QT corrected by Fridericia's formula              |
| RP2D         | Recommended Phase 2 Dose                          |
| SAE          | Serious adverse event                             |
| SAP          | Statistical analysis plan                         |
| SLL          | Small Lymphocytic Lymphoma                        |
| SOC          | System organ class                                |
| SPD          | Sum of the product of the perpendicular diameters |
| SRC          | Study Review Committee                            |
| TEAE         | Treatment-emergent adverse event                  |
| TFLs         | Tables, figures, and listings                     |
| TLS          | Tumor Lysis Syndrome                              |
| WHO          | World Health Organization                         |

## **1. INTRODUCTION**

This Statistical Analysis Plan (SAP) is created based on Protocol ME-522-001 (Original version, 05 December 2017, Amendment 1, 02 January 2018, Amendment 2, 15 August 2018, Amendment 3, 22 October 2018, Amendment 5, 28 January 2019, Amendment 7, 06 January 2020, and Amendment 11, 17 June 2022) and it describes in detail the statistical methodology and the statistical analyses to be conducted for the aforementioned protocol. The mockup shells of the Tables, Figures, and Listings (TFLs) for the statistical analysis will be described in a stand-alone programming specification document, which will be finalized before the database lock.

## **2. STUDY OBJECTIVES**

### **2.1 Primary Objectives**

The primary objectives of this study are as follows:

- Determine the safety and tolerability of voruciclib and identify a safe and minimum biologically effective dose (mBED) of voruciclib monotherapy in subjects with relapsed or refractory B-cell malignancies and relapsed or refractory acute myeloid leukemia (AML)
- Determine the safety and tolerability, and identify the safe and mBED of voruciclib in combination with venetoclax in subjects with relapsed or refractory AML

### **2.2 Secondary Objectives**

The secondary objectives of the study are as follows:

- Evaluate the potential efficacy of voruciclib monotherapy based on:
  - International Workshop on Chronic Lymphocytic Leukemia (IWCLL) criteria for CLL/SLL or the Lugano classification of response assessment for lymphoma, as appropriate, for subjects with B-cell malignancies
  - The 2017 European LeukemiaNet (ELN) criteria for subjects with AML
- Evaluate the potential efficacy of voruciclib in combination with venetoclax in subjects with AML based on the 2017 ELN criteria
- Evaluate the pharmacokinetics (PK) of voruciclib administered as monotherapy, and the PK of voruciclib and venetoclax when administered in combination

### **2.3 Exploratory Objectives**

The exploratory objectives of the study are as follows:

- Determine the effect of voruciclib monotherapy and voruciclib in combination with venetoclax (AML only) on biomarkers and functional activities of proteins in the apoptotic pathway
- Correlate anti-tumor activity with baseline tumor characteristics

### 3. STUDY DESIGN

#### 3.1 General Study Design and Plan

##### 3.1.1 Overall Study Design

This is a Phase 1, open-label, 3 + 3 dose escalation study to determine the safety and preliminary efficacy of the cyclin-dependent kinase 9 (CDK9) selective inhibitor voruciclib in subjects with relapsed/refractory B cell malignancies and AML, and in combination with venetoclax in subjects with relapsed/refractory AML after treatment with standard therapy.

Initially 3 subjects will be enrolled into a dose cohort and followed for 28 days. Due to the likelihood of subjects with advanced malignancy discontinuing between the start of the informed consent process and before completion of the first 28-day cycle for reasons unrelated to voruciclib toxicity, a fourth subject may be enrolled. This will mitigate the risk of delay in assessing each dose level. If a fourth subject is enrolled, the dose limiting toxicities (DLT) period will close when 3 subjects have completed 28 days without DLT. If one DLT occurs in any of the four subjects during the DLT assessment period, an additional 2 subjects will be enrolled to a total of 6 subjects.

Voruciclib will be administered once daily in 28-day cycles, with the first day of treatment designated as Day 1. The initial dose level in this current study was 50 mg voruciclib daily in Cohort 1, followed by additional dose cohorts increasing stepwise up to 250 mg (i.e., 50, 100, 150, 200, and 250 mg). Due to DLT at 100 mg QD, intermittent dosing regimens are being studied at 100, 150, or 200 mg on an intermittent schedule (IS) of two weeks on therapy followed by two weeks off therapy (IS2w,2w) or an IS of one week on therapy followed by three weeks off therapy (IS1w,3w). The previously planned maximum daily dose of 250 mg was based on data from previous clinical studies which indicate that the dose is tolerated (less than the previously identified MTD of 350 mg daily).

Dose cohorts planned prior to Amendment 7 are defined in Table 3-1:

